4.6.2. Adverse Events of Special Interest

Adverse events of special interest (AESI) are AEs (serious or non-serious) required to be monitored, documented, and managed in a pre-specified manner as described in the protocol. In this study, AESI are listed below (as provided in the protocol), along with each AESI detailed definition:

- Grade 3 or greater injection site reactions or hypersensitivity reactions including but not limited to anaphylaxis, laryngeal/pharyngeal edema, severe bronchospasm, chest pain, seizure, or severe hypotension (eCRF specific tick box on the AE page)

4.6.3. Events Causing Death

Subject deaths are per the observation periods will be summarized as follows.

- Deaths during the TEEAP
- Deaths during the TEFUP
- Deaths during the overall study period

4.6.4. Laboratory Safety Variables

Samples for laboratory testing will be collected at visits according to the schedule of events tables in the protocol. Samples will be analyzed by a central laboratory. The clinical laboratory data consists of serum chemistry, hematology, urinalysis and other specified in section 9.2.3.2 of the protocol.

Clinical laboratory values will be converted and analyzed in both standard international (SI) units and US conventional units provided by the central laboratory. Both actual test values and “change from baseline” values (defined as the post-baseline value minus the baseline value) over time will be summarized, where the post-baseline visits will be assigned to the Global Analysis Windows (See Section [6.4](#)).

Potentially clinically significant values (PCSV) ranges will be applied to the laboratory test values as applicable (see PCSV criteria in Appendix [10.3](#)).

Vital Signs

Both actual test values and “change from baseline” (defined as the post-baseline value minus the baseline value) over time in vital signs parameters (e.g., weight (kg), height (cm), BMI (kg/m²),

temperature ($^{\circ}\text{C}$ or $^{\circ}\text{F}$), pulse rate (beats/min), and systolic and diastolic blood pressure (mmHg)) will be summarized as laboratory safety variables. Potentially clinically significant values (PCSV) ranges will be applied to the vital sign parameter values as applicable (see Appendix 10.3 for PCSV criteria).

4.6.5. Physical Examination Variables

Physical examination will be conducted as the protocol scheduled visits. If any abnormal findings during the screening period, they will be recorded in medical history eCRF form and AE eCRF form for any findings during post-screening period.

4.7. Pharmacokinetic Variables

The pharmacokinetic variables are the concentrations of REGN10933 and REGN10987 in serum and time when a sample was collected. The sampling time points for dense and sparse collection schedules are specified in the schedule of events tables in the protocol.

4.8. Immunogenicity Variables

The immunogenicity variables are ADA status, titer, NAb status, and time-point/visit. Serum samples for Immunogenicity will be collected at the clinic visits specified in the schedule of events tables in the protocol.

5. STATISTICAL METHODS

For continuous variables, descriptive statistics will include the following: the number of subjects reflected in the calculation (n), mean, median, standard deviation, minimum, and maximum. For categorical or ordinal data, frequencies and percentages will be displayed for each category.

Baseline is defined as the last assessment obtained before the first dose of study drug.

Statistical hypotheses will be performed in seronegative subjects in Cohort A and Cohort B independently with separate type I error controls.

5.1. Demographics and Baseline Characteristics

Demographic and baseline characteristics will be summarized descriptively by treatment group and overall, for the study. These will be analyzed by cohort for both seronegative mFAS and SAF populations.

5.2. Medical History

Medical history will be summarized by SOC and PT and by treatment group and all groups combined for the seronegative mFAS populations defined in Section 3.1.

5.3. Prior/concomitant Medications or Procedures

All prior medications will be descriptively summarized by treatment group and overall, for the study, for subjects in SAF population.

Summaries will present subject counts (and percentages) for all prior medications, by decreasing frequency of the overall group incidence of ATC followed by ATC level 2, ATC level 4 and preferred term. For prior procedure, summaries will be by SOC and PT, sorted by decreasing frequency of SOC and PT based on the incidence in the overall group incidence. Subjects will be counted only once for each SOC and PT linked to the procedure.

All concomitant medications/procedures will be descriptively summarized by treatment group and observation period defined in Section 4.6.1, for subjects in SAF.

5.4. Prohibited Medications

Listing of prohibited medications described in Section 4.4 will be provided for subjects in SAF.

5.5. Subject Disposition

Subject study status will be summarized by treatment group and overall for the study.

The following will be provided:

- Number of screened subjects, defined as signed the ICF
- Number of randomized subjects
- Number of subjects randomized but who did not receive study treatment
- Number of subjects who discontinued the study, and the reasons for discontinuation

- A listing of subjects treated but not randomized, subjects randomized but not treated, and subjects randomized but not treated as randomized
- A listing of subjects prematurely discontinued from the study, along with reasons for discontinuation
- A summary of analysis sets including randomized subjects and randomized subjects by cohort, mFAS sets, SAF, PK, immunogenicity (ADA).

5.6. Extent of Study Treatment Exposure and Compliance

5.6.1. Measurement of Compliance

Subject treatment compliance is not applicable for this study, since the study drug is administered once at the site and will be the same as treatment exposure.

5.6.2. Exposure to Investigational Product

The duration of study treatment will be defined as 28 days after the last dose for a subject in SAF.

5.7. Analyses of Efficacy Variables

The following null and alternate hypotheses will be tested for the primary and secondary endpoints unless otherwise specified:

H0: There is no treatment difference between REGN10933+REGN10987 and placebo

H1: There is a treatment difference between REGN10933+REGN10987 and placebo

5.7.1. Analysis of Primary Efficacy Variables

Cohort A

The Cohort A primary efficacy endpoint described in Section 4.5.1 will be analyzed in the seronegative mFAS-A population. All post-baseline efficacy assessments obtained in the EAP will be included for the primary analysis.

In order to account for the correlation among subjects within a household and control the associated type 1 error inflation, a generalized linear model will be used to estimate the odds ratio between the treatment groups by using the GEE approach (See Appendix 10.4 for an example of SAS procedure). This model estimates a single within-household correlation coefficient. The model will include the fixed category effects of treatment group (placebo versus REGN10933+REGN10987), region (US versus ex-US), and age (≥ 12 to < 50 , ≥ 50 years). The model will use a compound symmetry covariance matrix and estimate the odds ratio between the treatment groups and corresponding 95% CI and p-value.

If the GEE model fails to converge due to most households containing only a single study subject in seronegative mFAS-A or the percentage of households in Cohort A with only a single study subject is 70% or more, then a logistic regression model will be used with treatment, region, and age group as fixed effects. The threshold of 70% was based on simulations of within-household correlation which show the type I error rate is inflated and the power is decreased when the

proportion of single-subject households is high (details provided in Section 6.6). If the logistic regression model does not converge, an exact logistic regression will be used. The estimates of odds ratio, the corresponding 95% CI and p-value will be provided from logistic regression (or exact logistic regression) for comparison of REGN10933+REGN10987 against placebo group.

In Cohort A, a subject will be considered having a symptomatic RT-qPCR confirmed SARS-CoV-2 infection (broad-term) during the EAP if any of the post-baseline RT-qPCR results during the EAP are positive with at least one symptom within 14 days of a positive RT-qPCR result (Section 4.5).

Cohort B

The Cohort B primary efficacy endpoint described in Section 4.5.5 will be analyzed in the seronegative mFAS-B population. The same statistical methods as described for Cohort A will be used to obtain the estimate of odds ratio and p-value for comparison between the treatment groups.

In Cohort B, a subject will be considered having a symptomatic RT-qPCR confirmed SARS-CoV-2 infection (broad-term) during the EAP if subjects have at least one symptom within 14 days of a positive RT-qPCR result at baseline or during the EAP.

Handling of Missing Central Lab SAR-CoV-2 RT-qPCR Data for Both Cohort A and Cohort B

Subjects with COVID-19 symptoms that are missing a central lab determined RT-qPCR test during the EAP (eg. are too sick to go to the study site) but have a positive SARS-CoV-2 test from a local lab (eg. in the hospital) will be considered as having a symptomatic infection if any of the symptoms occurred within 14 days of the positive SARS-CoV-2 test that was observed during the EAP.

The graphical display using Kaplan-Meier curve for the time to first symptom will also be provided.

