## 2. STUDY OBJECTIVES

All subjects in the study will be household contacts of the first known household member to be infected with SARS-CoV-2 infection (index case) but who are themselves asymptomatic (having no active respiratory or non-respiratory symptoms consistent with COVID-19) at the time of screening.

For analysis of endpoints, there are 4 defined cohorts based on the subjects' SARS-CoV-2 infection status at baseline, as measured by central lab SARS-CoV-2 RT-qPCR (quantitative reverse transcription polymerase chain reaction) and on the subject's age:

1. Cohort A: adult and adolescent subjects ( $\geq 12$  years) who are SARS-CoV-2 RT-qPCR negative at baseline
2. Cohort A1: pediatric subjects ( $< 12$  years) who are SARS-CoV-2 RT-qPCR negative at baseline
3. Cohort B: adult and adolescent subjects ( $\geq 12$  years) who are SARS-CoV-2 RT-qPCR positive at baseline
4. Cohort B1: pediatric subjects ( $< 12$  years) who are SARS-CoV-2 RT-qPCR positive at baseline

Results of the local diagnostic assay for SARS-CoV-2 from appropriate samples (eg NP, oropharyngeal [OP], or nasal or saliva) at baseline will be used as stratification factors for randomization and treatment group allocation, but not for the designation of cohorts for data analysis.

Cohorts are described in Section 3.2.3 and are defined in Section 6.1.6. Study objectives and endpoints are specified based on their SARS-CoV-2 RT-qPCR results at baseline: cohort A and cohort A1 (negative results) or cohort B and cohort B1 (positive results).

The “strict-term”, “broad-term”, and CDC definitions for signs/symptoms of SARS-CoV-2 infection are presented in Section 9.2.2.2.

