### 3.2.3. Enrollment by Baseline SARS-CoV-2 Infection

This study will include asymptomatic subjects regardless of baseline SARS-CoV-2 infection status or serologic status. Including all-comers into the study will provide important information on infection prevention through prophylaxis as well as the impact of pre-emptive therapy in infected but asymptomatic individuals. Since the primary efficacy objective in cohort A is focused on the prevention of symptomatic SARS-CoV-2 infection (broad-term), the primary population of interest are subjects that are seronegative and SARS-CoV-2 RT-PCR negative at baseline. It was estimated that approximately 10% of the study population for cohort A would be seropositive at baseline. However, blinded data review of approximately the first 25% of subjects enrolled shows that approximately 30% of subjects in cohort A are seropositive at baseline. Therefore, the majority of subjects enrolled are expected to be allocated to the primary study population of interest, seronegative and SARS-CoV-2 RT-PCR negative at baseline (ie, cohort A).

On day 1 and prior to randomization, subjects will have a local diagnostic assay for SARS-CoV-2 from an appropriate sample. Samples will also be collected for central lab SARS-CoV-2 RT-qPCR and serology tests. The results of the local lab tests will be available the same day and will be used as stratification for randomization to allow administration of study drug. In the event that local testing results are not anticipated to be available in the time required during screening, subjects may be randomized.

For data analysis, adult and adolescent subjects will be divided into 2 independent study cohorts: cohort A or cohort B. This allocation will be based on a central lab SARS-CoV-2 RT-qPCR test result performed during the screening/baseline visit. While stratification and randomization will be based on local test results, data analyses will be based on the central lab results of baseline SARS-CoV-2 RT-qPCR results from NP swab sample and the serological status.

The analysis of the adult and adolescent subject populations that are not part of the primary study population of interest (ie, those subjects in cohort A who are seropositive at baseline) will not contribute to a primary study objective or endpoint. These individuals will be analyzed separately either through secondary or exploratory objectives and endpoints.

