### **8.4. Method of Treatment Assignment**

Subjects will be randomized in a 1:1 ratio to receive REGN10987+REGN10933 or placebo according to a central randomization scheme provided by an interactive web response system (IWRS) to the designated study pharmacist (or qualified designee). Randomization will be performed by individual study subjects, not by households. In addition to a randomization number, all subjects randomized will be given a household identification number in the case that multiple members of the same household are enrolled and receive study drug. This ensures that any correlation among subjects within the same household may be considered in the statistical analysis. The REGN10987 and REGN10933 dose for adult, adolescent, and pediatric subjects is described in Section 8.1.

Randomization will be performed by site and stratified as follows:

- Local diagnostic assay for SARS-CoV-2 from appropriate samples (positive, negative, or undetermined)
- Age and/or weight:
  - <12 years and <10 kg,
  - <12 years and  $\geq$ 10 kg to <20 kg,
  - <12 years and  $\geq$ 20 kg
  - $\geq$ 12 years and <18 years
  - $\geq$ 18 years and <50 years
  - $\geq$ 50 years

Note that the cohorts used in the analysis are defined by the baseline central lab SARS-CoV-2 RT-qPCR results, not by the local diagnostic assay.

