2. INVESTIGATION PLAN

2.1. Study Design and Randomization

This is a phase 3 randomized, double-blind, placebo-controlled study in adults/adolescent subjects (≥ 12 years) and pediatric subjects (< 12 years of age) who are household contacts of the first known household member infected with SARS-CoV-2 (index case). All subjects in the study are asymptomatic (having no active respiratory or non-respiratory symptoms consistent with COVID-19) at the time of screening. The index case will have a diagnosis of SARS-CoV-2 infection using a diagnostic test, e.g., RT-PCR, antigen test, or other test format (approved or with Emergency Use Authorization issued by the US FDA or by local health authority). Randomization will be performed by individual study subjects, not by households. Some of the index cases of household contacts in this study may be participating in a separate treatment study (R10933-10987-COV-2067).

[figure not shown]
Randomization will be performed by site and stratified for assigning subjects in a 1:1 allocation ratio to placebo or REGN10933+REGN10987 [1200 mg (600 mg of each mAb SC). Randomization stratifications are test results (positive, negative, or unavailable) of a local diagnostic assay for SARS-CoV-2 (e.g., molecular assay such as RT-PCR assay for SARS-CoV-2 or a SARS-CoV-2 antigen test) from appropriate samples, e.g., nasopharyngeal (NP), oropharyngeal (OP), nasal, or saliva, and age group (< 12 years, ≥ 12 to < 18 years, ≥ 18 to < 50 years, or ≥ 50 years). For pediatric subjects (< 12 years), the weight group (≥ 20 kg, ≥ 10 to < 20 kg, and < 10 kg) will be used as an additional stratification factor.

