4.1. Demographic and Baseline Characteristics

The following demographic variables will be summarized:

- Age in years (continuous and categorical variable for subjects ≥ 12 years will be categorized as follows: ≥ 12 to < 18 , ≥ 18 to < 50 , ≥ 50 to < 65 , ≥ 65 to < 80 , ≥ 80 years)
- Sex (Male, Female)
- Race (American Indian or Alaskan Native, Asian, Black or African American, Native Hawaiian or Other Pacific Islander, White and Other, where “Other” may include, for example, not reported, unknown, and multiracial, etc.)
- Ethnicity (Hispanic or Latino with further subgroups [Black Hispanic or Latino and White Hispanic or Latino], not Hispanic or Latino with further subgroups [Black not Hispanic or Latino and White not Hispanic or Latino], not reported, and unknown)

Baseline characteristic variables include:

- Weight (kg) (quantitative and qualitative variable for pediatric subjects: < 10 , ≥ 10 to < 20 , and ≥ 20)
- Height (cm)
- Body mass index (BMI) (kg/m^2) (quantitative and qualitative variable for subjects ≥ 12 years: < 30 and ≥ 30)
- Randomization strata: local RT-qPCR status and age
- Region (US vs ex-US) and country
- Total household size including the house member(s) not participating this study
- Number of study subjects within household and cohort
- Index case interaction and household risk factors (e.g., share a bedroom, share a common room, no one wears a mask in home, etc.) per eCRF
- Status of index case participating R10933-10987-COV-2067
- Total household members, including index case, who participate the R10933-10987-COV-2067
- Infection risks (e.g. healthcare worker (Yes/ No), received influenza vaccine in last 14 days (Yes/No), first responder (Yes/No), Need to contact strangers on a regular basis (Yes/No), etc.) per exposure risk factors eCRFs

- Baseline overall serology status and observed combinations of three serology antibody assays
- Viral load (log10 copies/mL) at baseline for subject in cohort B
- Days between baseline central RT-qPCR test and study drug administration
- Baseline high risk subjects with at least one of the following criteria:
 - ≥ 65 years of age
 - BMI ≥ 35
 - Chronic kidney disease
 - Diabetes
 - Immunosuppressive disease
 - Are currently receiving immunosuppressive treatment

Are ≥ 55 years of age AND have cardiovascular disease OR hypertension OR chronic obstructive pulmonary disease

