6.5. Pooling of Centers for Statistical Analyses

Currently, the randomization is stratified by site. Since a potential differential treatment effect among countries may exist, region variable as a fixed effect factor will be included in the statistical analysis model. A subgroup analysis regarding region will also be performed for the primary efficacy endpoint. Results will also be summarized descriptively by country.

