10.4. Example of SAS Procedures for Primary Analysis and Missing Data Imputations by FCS

Primary Analysis - GEE Model

Below is an example of SAS code using a generalized linear model to estimate the odds ratio between the treatment groups with the generalized estimation equation (GEE) approach after 100 imputations.

```
proc genmod data=DATA_IN;
class treatment(ref='0') Age_group region; /*eg.treatment= 0:placebo */
by _imputation_;
model response(event='1') =treatment region age_group/dist=bin link=logit;
repeat subject=household_id/type=cs;
lsmeans treatment/diff om cl ilink;
ods output diffss=logOR geeexchcorr=icc;
run;
```

Primary Analysis - Logistic Regression Model

Below is an example of SAS code using a logistic regression model instead of using GEE approach when the percentage of households with a single study subject is 70% or more to estimate the odds ratio between the treatment groups after 100 imputations.

```
proc genmod data=DATA_IN descending;
class treatment(ref='0') Age_group region;
by _imputation_;
model response(event='1') =treatment region age_group/dist=bin link=logit;
lsmeans treatment/diff om cl ilink;
ods output diffss=logOR ParameterEstimates=parameterestimates;
```

run;

Missing Data Imputations – FCS

Assume the missing RT-qPCR test results occurred across Visit 5 (Day 8) to Visit 8 (Day 29) (e.g. 1=positive vs 0=negative). An example of SAS code for FCS MI with the random seed=2069 is presented below.

```
proc mi data=DATAIN out=DATAOUT seed=2069 nimpute=100;
class treatment age_group region v5 v6 v7 v8;
var treatment age_group region v5 v6 v7 v8;
fcs logistic(v5/LIKELIHOOD=AUGMENT);
fcs logistic(v6/LIKELIHOOD=AUGMENT);
fcs logistic(v7/LIKELIHOOD=AUGMENT);
fcs logistic(v8/LIKELIHOOD=AUGMENT);
run;
```

After FCS MI to generate 100 complete datasets, each subject's overall RT-qPCR test status during the EAP can be determined by any of imputed value V5 to V8 is equal to 1. The same model using GEE approach or logistic regression for the primary analysis will be applied.

The results from the 100 analyses will be combined using Rubin's formulae through PROC MIANALYZE procedure shown below.

```
proc mianalyze data=logOR;
ods output parameterestimates=final_logor;
modeleffects estimate;
stderr stderr;
run;
```

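### The local SARS-CoV-2 result stratifies randomisation but is missing from the cohort A and B primary models; adding it could gain a little power (roughly 0 to 1.4 points) if it is prognostic

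*SAP*

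**What the plan says.** Protocol 8.4 randomises by site and stratifies by "Local diagnostic assay for SARS-CoV-2 from appropriate samples (positive, negative, or undetermined") and by age (with weight bands for children under 12). SAP 2.1 agrees: "Randomization stratifications are test results (positive, negative, or unavailable) of a local diagnostic assay for SARS-CoV-2". The third level is called undetermined in one document and unavailable in the other; I treat it as the same level.

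The cohort A primary model in SAP 5.7.1 reads: "The model will include the fixed category effects of treatment group (placebo versus REGN10933+REGN10987), region (US versus ex-US), and age", with age in two levels. Cohort B uses the same methods, and Protocol 11.4.3.1 matches. The logistic fallback has the same covariates, and so does the example code in SAP Appendix 10.4: "model response(event='1') =treatment region age_group/dist=bin link=logit".

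For site, SAP 6.5 gives its reasoning: "region variable as a fixed effect factor will be included in the statistical analysis model". For the local result, the only planned use outside randomisation is descriptive: SAP 4.1 lists "Randomization strata: local RT-qPCR status and age" among the baseline characteristics. It appears in neither the sensitivity analyses (SAP 5.7.1.1) nor the subgroups (SAP 5.7.1.2).

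Two protocol statements bear on the reason. Section 3.2.3: "While stratification and randomization will be based on local test results, data analyses will be based on the central lab results". Section 2 says that local results "will be used as stratification factors for randomization and treatment group allocation, but not for the designation of cohorts for data analysis".

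**The concern.** A factor is usually chosen for stratification because it may predict outcome, and the usual practice is then to carry it into the model. Here one stratification factor has no counterpart.

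The two protocol statements settle who belongs to which cohort. They do not say which covariates enter the model once the cohort is formed. Within a cohort the local result can differ from the central one: the local assay may be an antigen or PCR test on one of several sample types (Protocol 9.2.1.2), and it may be waived (Protocol 6.1.3). A locally positive, centrally negative subject may be in early infection. A locally negative, centrally positive subject may carry less virus. Either could be prognostic, but the documents do not show that it is.

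What is at stake is precision: a prognostic covariate that is already recorded would be left unused.

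**Working it through.** **1. The plan's own figures.**
- Cohort A (SAP 2.2.1): 1248 subjects, 10% versus 5%, two-sided 0.05. A pooled z test with 624 per arm gives power 0.919. A GEE simulation (430 households, household correlation 0.1, about 400 runs) gives 0.905, standard error about 0.014. The plan states 0.914. Enrolment: 1248 / (0.9 × 0.7) = 1981, against 1980 stated.
- Cohort B (SAP 2.2.2): 200 subjects, 50% versus 25%. Exact two-sided Fisher power with 100 per arm is 0.945, so the stated >90% is reproduced.

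**2. Assumptions the documents do not supply.** Let s be the local-positive share within a cohort and RR the risk ratio of local-positive to other subjects. With the arm's overall rate p held at plan, p(other) = p / (1 − s + s·RR) and p(positive) = RR × p(other). In cohort A, RR is capped at 5. At p = 10% this puts the local-positive placebo rate at 5 × 0.10 / 1.2 = 42% (s = 5%) or 5 × 0.10 / 1.4 = 36% (s = 10%), below the 50% assumed for cohort B. Cohort B uses RR 1 to 2 and s of 50 to 90%. Treatment RR is 0.5 in each level.

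**3. Logistic comparison.** Logit(risk) = b0 + b1·treatment, without and with + b2·local result; Wald test on b1; 30,000 runs per cell; region and age effects not modelled. Power, without → with the term:

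| Cohort, rates | s | RR | Arms balanced within local result | Simple randomisation within it |
|---|---|---|---|---|
| A, 10% v 5% | 5% | 1 | 0.923 → 0.923 | – |
| A, 10% v 5% | 5% | 5 | 0.926 → 0.932 | 0.926 → 0.935 |
| A, 10% v 5% | 10% | 5 | 0.931 → 0.936 | 0.924 → 0.937 |
| A, 3.6% v 1.8% | 5% | 5 | 0.478 → 0.493 | – |
| B, 50% v 25% | 50% | 2 | 0.965 → 0.970 | 0.959 → 0.971 |
| B, 50% v 25% | 70% | 2 | 0.962 → 0.966 | 0.958 → 0.965 |

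The 3.6% is the placebo rate in the administrative assessment (8/223, Protocol 3.2.5); 1.8% is half of it. Over all cells, with differences taken before rounding, cohort A at s = 5 to 10% and RR 2 to 5 gains 0.0 to 1.4 points. Cohort B at RR 1.5 to 2 gains 0.1 to 0.5 points balanced and 0.1 to 1.3 points unbalanced. At RR 1 the change lies between −0.1 and +0.01. A separate run of the main cells gave the same picture within simulation noise. If the cohort B effect were weaker than planned (50% v 30%, s = 50%, RR 1.9), the gain would be about 1 point balanced and 2 points unbalanced.

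**4. GEE comparison.** This used an exchangeable GEE with robust errors, latent household correlation 0.3, blocks of 4 within site (100 assumed) × age × local result, and 30% then removed as seropositive. There were 430 households in A and an assumed 160 in B.
- A, 10% v 5%: s = 5%, RR 5, 0.937 → 0.944; s = 10%, RR 5, 0.940 → 0.950; s = 5%, RR 1, 0.932 → 0.930.
- A, 3.6% v 1.8%: s = 5%, RR 5, 0.507 → 0.512.
- B: s = 70%, RR 2, 0.965 → 0.973; s = 70%, RR 1, 0.965 → 0.964; s = 90%, RR 2, 0.967 → 0.967.

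The simulation error of these differences is 0.15 to 0.5 points.

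**5. Type I error.** In the logistic runs with exact balance within local result, cohort A at RR 5 gives 0.041–0.042 without the term and 0.049–0.050 with it. In the GEE runs (3000 each; standard error √(0.05 × 0.95 / 3000) = 0.004) the values are 0.059 → 0.057 and 0.054 → 0.053 in A, and 0.054 → 0.050 in B.

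**6. Sparseness.** At s = 5%, cohort A has 62 local-positive subjects, 31 per arm. At 3.6% v 1.8% and RR 1, the chance of no event among them is 0.964^31 × 0.982^31 = 0.18 (19% of simulated runs). At RR 2 and RR 3 it is 3.7% and 0.9%. In cohort B the local coefficient was not estimable in at most 1.2% of runs.

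**The case against.** The strongest reply is that this is a preference and not a defect. Both share and prognostic strength are assumed, and in the GEE runs the gains above 0.5 points come only at the top of the assumed range. That is true, and it is why the point is optional.

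The second reply is that the term carries risk. SAP 5.7.1 sends a logistic model that does not converge to exact logistic regression. If separation on the local result triggered that step, power in the affected runs would fall from 0.465 to 0.428. At 3.6% v 1.8%, s = 5% and RR 1, that costs 0.19 × 3.7 = 0.7 points overall. The GEE fallback rule covers single-subject households, not separation. The infection endpoint is analysed with the primary model after imputation (SAP 5.7.3), so changing one model alone would make the two inconsistent. Subgroup fits reuse the primary model. All of this stands and shapes the fix.

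Third, related questions are already probed: the 72-hour exclusion in cohort A and the baseline viral-load subgroup in cohort B. These help interpretation but do not adjust the primary test.

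A reader might also infer that the present test is materially conservative. That needs balance within local result after subjects are split by central PCR and serology, which allocation by site, age and local result does not guarantee. The GEE runs show no conservatism.

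**Conclusion.** The omission is factual, and the documents do not explain it. If the local result is prognostic within a cohort, including it gains roughly 0 to 1.4 points of power at the rates studied, in either cohort; if not, the change is about zero. This rests on assumed shares (5–10% local-positive in A, 50–90% in B) and assumed risk ratios. At 1–3% local-positive (12 to 37 of 1248) the term would be too sparse to keep in cohort A, and nothing would change there.

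Three stronger readings are not supported. Validity is not in question: type I error is much the same with and without the term in the GEE runs. The stated power above 90% is reproduced without it. Nor can the benefit be placed mainly in cohort B: the ranges for the two cohorts overlap almost entirely, and the documents give no discordance rate to separate them.

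**What to change.** Before the first-step database lock, on blinded data (SAP 1 allows such revisions):

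- Add local result (positive versus negative or undetermined) as a fixed effect in the cohort A and B primary models, in the binary secondary models that use the same approach, and in the Appendix 10.4 code.
- Add the same term to the FCS imputation model for the infection endpoint.
- Keep the term in a given fit, subgroup fits included, only if blinded pooled counts show a prespecified minimum of subjects and at least some events and non-events in each level. A head count alone is not enough, as the 62-subject case shows.
- If that fails, or the coefficient is not estimable, revert to treatment, region and age. Do not move to exact logistic regression for this reason.
- Report the model without the term as a sensitivity analysis.

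Tabulation by cohort and arm is already planned (SAP 4.1 and 5.1) and needs no change. This point does not extend to the Van Elteren tests.

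The variable is already in the CRF (Protocol 9.2.1.2). The costs are one degree of freedom, the extra rule, and an odds ratio conditional on local result (in one cohort A GEE simulation, with a local-result odds ratio of 5, it moved from 0.475 to 0.464). Pooling undetermined with negative also dilutes the term: in cohort B with 15–25% undetermined and RR 1.5 to 2, the gain is 0.0 to 0.3 points, against 0.0 to 0.5 with three levels.
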